Hysterectomy is one of the most common surgical procedures performed in the United States, with more than 600,000 done annually. Over the last decade, there has been major changes in regards to the surgical approach utilized. With the advent of laparoscopy and robotic surgery, the rate of procedures done vaginally or abdominally has decreased significantly. One of the major drivers to this change is the demand for a faster recovery and decreased postoperative discomfort. Additionally, several adjuvant methods such as a TAP (transverse abdominal plain) block, ERAS (expedited recovery after surgery) pathway, etc. have been developed in order to minimize pain after surgery and hence increase patient satisfaction. Paracervical block is a particular technique that has been evaluated in multiple studies as a way to reduce pain after vaginal surgery. Studies have been successful in demonstrating an improvement in pain scores after these types of procedures. However, to our knowledge, there has never been follow-up to evaluate this method during the laparoscopic approach, with or without robotic assistance. The rationale of why this technique may be beneficial during a hysterectomy is that after infiltrating the cervical stroma with local anesthetic, it will diffuse towards the pelvic sidewalls via the lymphatic and capillary systems, which would allow for the anesthetic agent to come in direct contact with the nerve plexuses that innervate the pelvic structures. Safety of the technique has been proven over the years, given that it is widely used during office procedures that involve manipulation of the cervix. Although much of the focus regarding reducing postoperative pain has been centered on the abdominal wall and port sites, it is undeniable that a significant portion of pain actually arises from the pelvic surgical site; particularly since laparoscopic trocars have become smaller, resulting in less trauma. Our aim is to determine if infiltrating the cervical stroma with local anesthetic prior to performing a hysterectomy will reduce postoperative pain scores, and hence increase patient satisfaction.

Methods

Study design

This is a prospective randomized controlled trial in which patients that are scheduled to undergo a laparoscopic hysterectomy would be allocated to one of two groups: Paracervical block with local anesthetic (bupivacaine 0.5%), or placebo. This would be achieved using block randomization. The

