- Preoperative indication for surgery (pain, prolapse, tumor, bleeding, etc)
- Procedures performed (if ovaries/tubes were removed, if robotic assistance was used, if any additional procedures that are exceptions from the exclusion criteria were performed).
- Specimen weight
- Uterine pathology
- Pain score at 30 minutes (see appendix 1 for Wong-Baker scale)
- Pain score at 60 minutes
- Number of days in the hospital (zero if discharged on same-day)

Data Handling

A master key will be generated during randomization. It will contain patient initials and medical record number, and an individual code. Only the primary investigator will have access to this master key.

A separate de-identified database using the individual code as index will be used for collection of all data points. The data that can be collected on the day of surgery (baseline characteristics, operating time, pain scores, etc) will be collected that day using a standardized form (appendix 2). This will later be transferred to the de-identified database. Using the master key, we will research pathology reports when available to complete final data points (uterine weight, histology, etc).

The data-collection sheets will be destroyed as soon as they are transferred into the de-identified database.

Data Analysis

We will use T-Student tests to assure groups are homogenous to age, BMI, operating time, history of cesarean deliveries, and uterine weight. ChiSquare and Ancova analysis will be utilized to determine if there is a significant difference in reported pain scores between groups. We will also stratify subjects based on uterine

weight, history of cesarean delivery, additional procedures, etc. and determine if this has an effect on the reported pain scores.

Time Frame

We expect to be able to consent and enroll at least two patients per week (average range of hysterectomy procedures per week from the surgeons that will participate is 5-10). We expect the data collection phase to span over 30 weeks approximately.

Strength/Innovation

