Patient satisfaction is a center point in today's healthcare. Faster recovery with less discomfort is not only standard of care, but may also translate into major economic advantages, such as less narcotic use and a decreased rate of postoperative admission. Using this technique as an adjuvant treatment for pain after laparoscopic hysterectomies has never been explored. There is data published for similar procedures, which demonstrates a clear benefit. If this study demonstrates significant improvement in pain scores, it has the potential to change standard of care for pain control during hysterectomy procedures.

Limitations

The main confounding factors are difference in operating style between surgeons and baseline surgical characteristics (large uteri that may require more dissection and tissue manipulation, etc.). To control for this we are only recruiting patients from 3 surgeons who have a similar operating technique. In addition to this, we are documenting operating time and specimen weight, which can be used to compare both groups and assure that they are homogenous to these potential confounders. Further analysis will also be made specifically stratifying the data based on these characteristics.

Risks

The risks of the procedure are minimal. Regarding possible adverse reactions to the local anesthetic, there is no additional risk given that this is already routinely administered during surgery. Patients will be screened to confirm they do not have a history of allergies to the medication. Possible reactions include hypotension, bradycardia, headaches, tremors, etc.

The paracervical block is routinely performed in the office setting before most invasive procedures involving the cervix, and risks are minimal, similar to those involving any subdermal injection. Possible risks include bleeding from injection site.

There is also the potential risk of accidental disclosure of the health information that will be collected.

Benefits

This study may find new methods of improving postoperative analgesia for patients undergoing minimally invasive hysterectomy procedures which may lead to less narcotic use, faster discharge from hospital, and greater satisfaction.

Costs

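### Surgeon is named first among the main confounders, but no stratification by surgeon is described and surgeon is neither recorded nor listed for analysis, so chance imbalance could go unseen and some precision can be lost

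*Combined protocol and SAP*

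**What the plan says.** All references are to the combined protocol and SAP.

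- **Limitations** names the problem: "The main confounding factors are difference in operating style between surgeons", followed by baseline surgical characteristics. The remedy follows at once: "To control for this we are only recruiting patients from 3 surgeons who have a similar operating technique". The section adds "we are documenting operating time and specimen weight, which can be used to compare both groups", and promises further stratified analysis on these characteristics.
- **Methods, Study design** describes allocation to the two groups in one sentence: "This would be achieved using block randomization". It gives no block size, list structure or stratification factor.
- **Data Collection** and the **Appendix 2** form cover age, BMI, operating time, cesarean history, indication, procedures, specimen weight, pathology, pain scores and hospital days. Operating surgeon is in neither place.
- **Data Analysis** plans balance tests: "We will use T-Student tests to assure groups are homogenous to age, BMI, operating time, history of cesarean deliveries, and uterine weight". For the main comparison, "ChiSquare and Ancova analysis will be utilized to determine if there is a significant difference in reported pain scores between groups"; no ANCOVA covariate is named. The stratified analyses name uterine weight, cesarean history and additional procedures, and the list ends open.
- **Data Handling** says the paper forms are destroyed once transferred to the de-identified database.

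**The concern.** The plan identifies a prognostic factor with three known levels, fixed before each case, and then does not carry it into the allocation, the data or the analysis. Blocks on a single list balance the arm totals; they do not balance the arms within each surgeon. Operating time and specimen weight are only partial stand-ins for surgeon.

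Two things are at stake. First, in a small trial one arm may by chance hold many more of one surgeon's patients, and a reader will ask whether the pain difference reflects the block or the surgeon. The planned dataset could not answer. Second, any between-surgeon variation stays in the error of the arm comparison, although it could be removed cheaply.

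**Working it through.** **Inputs from the document.** Sample Size gives mean 6, SD 2, a 40% reduction (0.40 × 6 = 2.4 points), 5% significance, 80% power and a sample of 32. Limitations gives three surgeons.

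**Assumptions, because the document is silent.** 1:1 allocation; blocks of 4; surgeon shares equal or 50/30/20; two-sided test; 32 as the total, with 32 per arm as the alternative. The size of any surgeon effect is also assumed: a step of *d* points between adjacent surgeons (effects −*d*, 0, +*d*).

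**1. The plan's own figure.** Per arm, n = 2(1.96 + 0.84)² × 2² / 2.4² ≈ 10.9, so 11 per arm (22 in total), or 12 per arm (24) by the t-test. The stated inputs do not give 32. That is a separate matter. Taking 32 as the total (16 per arm), power for 2.4 points is 92% by the normal approximation and 91% by the t-test.

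**2. How often surgeon mix is uneven.** This step needs no assumed surgeon effect. Simulating 32 patients with one unstratified list:

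- At least one surgeon with six or more patients is split 70:30 or worse in about 26-35% of trials, across runs and share patterns. Stratified by surgeon: 0%.
- With equal shares, some surgeon's share differs between arms by at least 25 percentage points (4 of 16 patients) in about 37-40% of trials. Stratified: 0%.

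**3. What uneven mix does to the estimate.** The variance of the surgeon effect is 2*d*²/3 with equal shares. With 50/30/20 it is (0.5 + 0.2 − 0.3²)*d*² = 0.61*d*². Without stratification, the SD of the arm difference due to surgeon mix alone is √(variance × 2/16).

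| Setting (equal shares) | SD of surgeon-mix difference | about 95% limit | as % of 2.4 |
|---|---|---|---|
| 32 in total, *d* = 0.5 | 0.14 | 0.28 | 12% |
| 32 in total, *d* = 1 | √(0.667 × 0.125) = 0.29 | 0.56 | 23% |
| 32 per arm, *d* = 1 | √(0.667 × 0.0625) = 0.20 | 0.40 | 17% |

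Stratified, with 32 in total and *d* = 1, simulation gives an SD of 0.08-0.09 and a limit of about 0.16-0.17.

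For scale, the standard error of the arm difference at 16 per arm is 2√(2/16) = 0.71. The 0.29 is part of that figure, not added to it, because the SD of 2 is taken to include surgeon variation.

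**4. Precision recoverable.** Surgeon's share of total variance is (surgeon variance)/4. Stratifying and fitting surgeon is worth 1/(1 − share) − 1 in patients:

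- *d* = 0: 0%.
- *d* = 0.5: share 4.2% (equal) or 3.8% (50/30/20), so about 4%.
- *d* = 1: share 16.7% or 15.3%, so 20% or 18%.

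**5. Power for 2.4 points, 32 in total (simulation, equal shares).**

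| Assumed surgeon share of variance | Unstratified, unadjusted | Unstratified, surgeon fitted | Stratified, surgeon fitted |
|---|---|---|---|
| 0% | 91% | 89% | 90% |
| 10% | 91% | 92% | 93% |
| 20% | 91% | 94% | 96% |

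**The case against.** **Silence is not a statement.** The Study design sentence does not say the list is unstratified, and a reader should not infer that it certainly is. This stands: the point is that stratification is not described. Nothing in the plan would, however, lead whoever prepares the lists to make three.

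**The surgeons were chosen to be alike.** A 1-point step puts two points between the extreme surgeons, a full SD and 83% of the target effect (2/2.4). That sits awkwardly with similar technique, and the smaller figures may be nearer the truth. This also stands, so no loss of precision can be asserted as fact. But a plan that ranks surgeon first among its confounders cannot take the surgeon effect to be nil.

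**The trial may be larger than 32.** Sample Size does not say total or per arm. Time Frame implies about 60 patients (2 per week × 30 weeks), which fits 32 per arm. The imbalance effect is then smaller, as the table shows.

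**Adjustment can correct imbalance afterwards.** True: fitting surgeon in the ANCOVA recovers much of any loss, so it would be wrong to say that imbalance cannot be undone. But surgeon must be recorded and specified, and it is neither. It might be traced through the master key and the medical record, or fall under the open-ended list of stratified analyses, but the plan provides for neither.

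**A reader might infer that the result is confounded or the trial underpowered.** The documents support neither. Randomization without stratification is unbiased, its chance imbalance is already within the standard error, and power for 2.4 points exceeds the planned 80%.

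**Conclusion.** The point holds as a gap between the confounder the plan ranks first and what it does about it. Restricting recruitment to three similar surgeons limits how much imbalance could matter, not how often it occurs. At 32 patients some unevenness in surgeon mix is likely, and a marked split has about a 26-35% chance, assuming blocks of 4. As written, that imbalance would be neither visible nor adjustable in the planned dataset.

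The cost in precision is conditional: nil to about 20% in equivalent patients over assumed steps of 0 to 1 point, and less in absolute terms if 32 is per arm. The trial's ability to detect 2.4 points is not threatened. The change is worth making because it is cheap and answers a question the plan itself raises. The firmest part is that surgeon is not recorded, which rests on no assumed effect.

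**What to change.** 1. **Study design:** state that block randomization is stratified by operating surgeon, with three lists. Use small block sizes that vary, and keep them out of documents seen by site staff. A fixed block size within each surgeon's list would make late assignments in a block deducible to anyone who knows the earlier ones. The surgeon is known before the syringe is prepared, so the stratum is available at allocation.
2. **Data Collection and Appendix 2:** add operating surgeon (coded 1-3), and carry it into the de-identified database.
3. **Data Analysis:** pre-specify surgeon as a factor in the ANCOVA of pain scores, so that the analysis follows the randomization.

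**Cost:** three lists instead of one, one form field and two degrees of freedom. Arm totals may differ by a few patients if last blocks are incomplete (with blocks of 4, at most 2 per surgeon, so 6). No extra patients are needed, and power is essentially unchanged if surgeons do not differ.

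**If stratified lists are not practical,** do steps 2 and 3 alone. That recovers much of any loss, at a cost of about 2-3 points of power if surgeons do not differ.

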intervention would be performed after the patient is under general anesthesia, prior to starting the surgery. Patients would be consented in the office or preoperative area (before receiving sedatives). As far as the intervention itself, it would consist of injecting 10 mL of 0.5% bupivacaine into the cervical stroma at 3 and 9 o'clock, which is standard technique for para-cervical block. The remainder of the procedure will then continue in a regular fashion. Alternatively, patients in the control group will be injected with 10 mL of normal saline. The surgeon would be blinded as to patient allocation. The formulations (saline or bupivacaine) will be previously prepared in a syringe in the operating room by a member of the research team prior to beginning the procedure. At the end of the case, pain will be assessed using a visual analogue scale with a range from 0 to 10 (Wong-Baker faces – appendix 1) by one of the researchers who will also be blinded to the group. This will be done at 30 and 60 minutes after surgical stop time. Additional pain control in the PACU will be standardized to all patients.

Study Subjects

Subjects will be selected based mainly on the fact they are undergoing a hysterectomy.

Inclusion criteria:

- Undergoing laparoscopic hysterectomy with or without salpingoophorectomy for benign indications
- Undergoing laparoscopic hysterectomy with robotic assistance with or without salpingoophorectomy for benign indications
- Between 18 and 60 years of age

Exclusion criteria:

- Intraoperative detection of malignancy
- Undergoing additional procedures at the time of surgery (except prophylactic McCall culdoplasty/uterosacral ligament suspension, excision of endometriosis, appendectomy, cystoscopy)
- Inability to perform paracervical block due to anatomic abnormalities (absent/flush cervix)
- Known allergy/sensitivity to bupivacaine
- Intraoperative bowel injury, bladder injury, ureter injury or major vessel injury that required repair.

Sample Size

Based on previous publications, it was determined that the expected mean pain score on postoperative day 0 after a TLH was 6 on the VAS, with a SD of 2. (10, 11) In order to detect

at least a 40% reduction in postoperative pain between groups, with a significance level of 5% and a power of 80%, a sample of 32 was required.

Data Collection

Data points to be collected are as follows:

- Age
- BMI
- Operating time
- History of cesarean deliveries

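### The plan records no adverse event, so its data can neither support nor contradict the premise that the local anesthetic adds no risk

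*Combined protocol and SAP*

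**What the plan says.** The Risks section calls the risks minimal. On reactions to the local anesthetic it states that "there is no additional risk given that this is already routinely administered during surgery", and the same paragraph continues: "Possible reactions include hypotension, bradycardia, headaches, tremors, etc". The next paragraph turns to the injection itself: "Possible risks include bleeding from injection site". Background/Significance gives the general premise: "Safety of the technique has been proven over the years, given that it is widely used during office procedures".

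The Data Collection section opens with "Data points to be collected are as follows" and lists 11 items: age, BMI, operating time, cesarean history, indication, procedures, specimen weight, pathology, pain at 30 minutes, pain at 60 minutes, and days in hospital. Appendix 2 is the form on which same-day data are entered. The Data Analysis section compares baseline and surgical characteristics and pain scores. Intraoperative injury needing repair appears only among the exclusion criteria.

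**The concern.** The protocol names specific harms but gives the trial no means of recording them. The block is the experimental intervention, and only the active arm receives bupivacaine through it; controls receive saline. A comparison by arm is therefore the one direct piece of evidence on harm that this design could produce, and the plan does not collect it.

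This matters because of how the result may be used. Strength/Innovation says that, if pain scores improve significantly, "it has the potential to change standard of care for pain control during hysterectomy procedures". The same section says that the technique has not been studied as an adjuvant in laparoscopic hysterectomy, so office experience is indirect support. Followed as written, the trial would report benefit by arm and nothing on harm by arm, and the statement about risk would be repeated without data from the trial.

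**Working it through.** **Step 1. Named harms against what is captured.** The Risks section names five events: hypotension, bradycardia, headaches and tremors for the anesthetic, and bleeding for the injection.

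- Data Collection list: 0 of 11 items records any of the five, or any other adverse event. Days in hospital is at most an indirect signal.
- Appendix 2: no field for any of the five. Its two free-text blanks for other entries belong to indication and pathology.
- Data Analysis: pain scores are the only outcome compared between arms.
- Data Handling: the collection sheets are destroyed after transfer, and the only later record look-up described is for pathology reports.

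The trial dataset would therefore hold no adverse event, whatever happened to the patients.

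**Step 2. Arm size.** The Sample Size section gives 32 without saying whether this is the total or per group. Its own inputs do not settle the matter. With mean 6 and a 40% reduction, the difference is 0.40 × 6 = 2.4. With SD 2, two-sided 5% and 80% power:

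n per arm = 2 × (1.960 + 0.842)² × 2² / 2.4² = 2 × 7.85 × 4 / 5.76 = 10.9, so 11 per arm and 22 in total.

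A t-test solution gives 12 per arm and 24 in total. Neither is 32. The Time Frame section expects at least two patients a week for about 30 weeks, or about 60 patients, which is nearer to 64 than to 32. Both readings are carried forward: 16 per arm and 32 per arm. Equal allocation is assumed, because the ratio is not stated.

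**Step 3. Chance that a reaction occurs in the block arm and is missed by the dataset.** Formula: 1 − (1 − r)^n. The documents give no event rates, so r is an assumption.

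| Assumed true rate r | n = 16 | n = 32 |
|---|---|---|
| 2% | 1 − 0.98^16 = 0.276 | 1 − 0.98^32 = 0.476 |
| 5% | 1 − 0.95^16 = 0.560 | 1 − 0.95^32 = 0.806 |
| 10% | 1 − 0.90^16 = 0.815 | 1 − 0.90^32 = 0.966 |

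**Step 4. What zero recorded events would show.** The one-sided 95% upper limit for 0 of n is 1 − 0.05^(1/n).

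- n = 16: 1 − 0.05^(1/16) = 0.171
- n = 32: 1 − 0.05^(1/32) = 0.089

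The upper end of the two-sided exact 95% interval is 1 − 0.025^(1/n), which gives 0.206 and 0.109.

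**Step 5. What a comparison by arm could detect.** For assumed rates of 5% and 20%, the usual normal approximation is Φ{[0.15 − 1.96 × √(2 × 0.125 × 0.875 / n)] / √[(0.05 × 0.95 + 0.20 × 0.80) / n]}. It gives power of about 24% with 16 per arm and 44% with 32 per arm. The approximation is rough at such small counts, but it shows that the data would be descriptive.

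**The case against.** The strongest case against the point is that safety is not an aim of this trial. The hypothesis and aims concern pain, the remark on standard of care is conditional on pain scores, and the pain comparison is unaffected by missing safety data. The added data could not establish safety either. All of that stands. It makes this a gap in reporting harm and an untested premise, not a failed endpoint.

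Several stronger readings are tempting, and the documents do not support them.

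- A reader might infer that the Risks section contradicts itself. It does not. It treats reactions to the anesthetic as a background risk of surgery in which the drug is already used, and then says what they are. The bleeding risk is in a separate paragraph about the injection, which the claim of no added risk does not cover.
- A reader might infer that the protocol says the block comes on top of the routine local anesthetic. No sentence says so. The inference is reasonable from Study design (the rest of the operation proceeds as usual), Risks and Costs (local anesthetic is routine in these operations). The documents do not say whether other local anesthetic is the same in both arms.
- A reader might infer that reactions would go unrecorded altogether. Clinical records may hold them; what is shown is that the trial dataset would not.
- Excluding patients with an organ or vessel injury concerns surgical complications and is not evidence of hidden drug reactions. It matters here only because the block precedes surgery, so these patients have already been injected.

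Two practical objections also stand. Undefined yes/no boxes for hypotension or bradycardia under general anesthesia would be hard to interpret, and the plan's only described assessments are the two pain scores, so intraoperative events need another source. Also, both arms are injected, so bleeding counts would describe the injection and not compare it with none. Finally, Appendix 2 is labeled an example, but the Data Collection list has the same gap.

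**Conclusion.** The concern holds as a gap in collection and reporting. The plan names five possible harms and captures none of them, so its data could neither support nor contradict the statement that the anesthetic adds no risk. That statement is an argument from routine use, and the trial leaves it untested.

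The gap itself depends on no calculation. Its size does: across assumed true rates of 2% to 10%, the chance of at least one missed reaction in the block arm runs from 28% to 81% with 16 per arm, and from 48% to 97% with 32 per arm. These figures rest on assumed event rates, equal allocation and the two readings of 32. Under either reading the trial is too small to establish absence of added risk, since zero events would leave rates up to about 17% or 9% unexcluded. Both collection and softer wording are therefore needed. The change should be made because it is cheap and bears on patient safety; it does not affect the validity of the pain result.

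**What to change.** 1. Add to the Data Collection list and to Appendix 2 a yes/no field for each named event (hypotension, bradycardia, headache, tremor, injection-site bleeding) and one for any other event.
2. State in advance a definition for each event, one time window (from injection to either the 60-minute assessment or discharge, chosen beforehand) and a source (existing anesthesia and PACU records).
3. Add to Data Analysis one descriptive table of counts by arm with exact 95% intervals, for all injected patients, including those later excluded for intraoperative injury. No significance test is needed.
4. Reword the sentence on no added risk as an assumption based on routine use, and say that the trial is too small to establish it.

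The cost is one extra table, some chart abstraction and a little more data entry. No change to dose or treatment is proposed.
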